#### **6.13.4. Clinical Laboratory Evaluation**

Laboratory evaluations will be summarized and analyzed for the following periods and populations:

- Period 2 prior to initiation of biologic rescue of ixekizumab 80 mg Q2W (Safety Population)
- Period 2 post initiation of biologic rescue of ixekizumab 80 mg Q2W (IR Population, for categorical safety analyses only)
- Period between Week 0 and Week 16 (Safety Population, for categorical safety analyses only)

Clinical laboratory assessments include hematology, serum chemistry, urinalysis, and safety-related immune markers such as neutrophil counts.

Treatment group comparisons will be conducted for Safety Population for Period 2 and the period between Week 0 and Week 16 using an ANCOVA model with treatment group and baseline value for continuous data and Fisher's exact test for categorical data as described in Section 6.1.2.1. Only categorical safety data will be summarized for the IR Population.

Continuous laboratory tests will be summarized as changes from baseline to last observation for patients who have both baseline and at least 1 postbaseline result for Periods 2 and 3, respectively:

- The scheduled visits/measurements will be included. The unscheduled visits and the repeat measurements will be excluded.
- Both international system of unit (SI) and conventional unit will be summarized when different.
- Data will be analyzed based on original scale.

Laboratory test observed values at each visit (starting at baseline) and change from baseline to each scheduled visit, respectively, will be displayed in box plots for patients who have both a baseline and at least one postbaseline result. These box plots will be used to evaluate trends over time and to assess a potential impact of outliers on central tendency summaries.

- The scheduled visits/measurements will be included. The unscheduled visits and the repeat measurements will be excluded.
- The displays with both SI and conventional units will be provided when different.
- The following summary statistics will be included as a table below the box plot: number of patients with a baseline and at least one postbaseline result, mean, SD, minimum, Q1, median, Q3, and maximum.
- Data will be summarized based on original scale.
- On the box plots of the laboratory test observed values, the lines of the reference ranges/limits (by using the performing laboratory reference ranges) will be added. In cases where limits vary across age and gender, the lowest of the high limits and the highest of the low limits will be used.

The number and percentage of patients with a treatment-emergent or follow-up emergent abnormal, high, or low for laboratory tests will be summarized by treatment group for each study period. The comparisons between and among treatment groups will be conducted using Fisher's exact test for the Safety Population for Period 2 and Period between Week 0 and Week 16.

- All scheduled, unscheduled and repeated measurements will be included.
- Performing laboratory will be used to define the low and high limits reference ranges except for leukocyte, neutrophil, lymphocyte and platelet counts, where Lilly defined lower limit of normal will be used for these 4 labs.
- Alanine aminotransferase (ALT), aspartate aminotransferase (AST), total bilirubin, alkaline phosphatase (ALP), neutrophils, leukocytes, platelets, and lymphocytes will not be included in the treatment-emergent abnormal, high, or low summary as a separate analysis addressing the risk of liver injury is described in Section 6.13.3.1 and a separate analysis addressing leukocytes (white blood cell [WBC]) and platelets is described in Section 6.13.4.1.
- Note that the ranges are defined by a lower limit of normal (LLN) and an upper limit of normal (ULN). A result that is greater than or equal to the LLN and less than or equal to the ULN is considered to be within the normal ranges.
- For categorical laboratory tests:
  - Treatment-emergent abnormal value is defined as a change from normal at all baseline visits to abnormal at any time postbaseline during the treatment period.
  - Follow-up emergent abnormal result is defined as a change from normal at baseline to abnormal at any time during the follow-up period.
- For continuous laboratory tests:
  - Treatment-emergent high value is defined as a change from a value less than or equal to the ULN at all baseline visits to a value greater than the ULN at any time postbaseline during the treatment period.
  - Treatment-emergent low value is defined as a change from a value greater than or equal to the LLN at all baseline visits to a value less than the LLN at any time postbaseline during the treatment period.
  - Follow-up emergent high value is defined as a change from a value less than or equal to the ULN at baseline to a value greater than the ULN at any time postbaseline during the follow-up period.
  - Follow-up emergent low value is defined as a change from a value greater than or equal to the LLN at baseline to a value less than the LLN at any time postbaseline during the follow-up period.

By-patient listing of laboratory test values will be provided. Listing of laboratory tests reference ranges (Lilly defined LLN for leukocyte, neutrophil, lymphocyte and platelet counts and Performing Lab reference ranges for other lab tests) will be provided. By-patient listing of abnormal laboratory test results (criteria defined in the shift tables excluding the normal category) for parameters of special interest (hepatic, leukocytes, and platelets) will be provided.

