### **9.5.2. Clinical Laboratory Tests**

Laboratory assessments will be presented as mean changes from baseline and as incidence of treatment-emergent abnormal, high, or low laboratory values (see below). Shift tables will be presented for selected parameters.

- For categorical lab tests:
  - Treatment-emergent **abnormal** value = a change from normal at all baseline visits to abnormal at any time postbaseline
- For continuous lab tests:
  - Treatment-emergent **high** value = a change from a value less than or equal to the high limit at all baseline visits to a value greater than the high limit at any time postbaseline
  - Treatment-emergent **low** value = a change from a value greater than or equal to the low limit at all baseline visits to a value less than the low limit at any time postbaseline

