### Clinical Laboratory Tests

| Hematologya:                                     | Serum Chemistrya:                                      |
|--|--|
| Hemoglobin   | Sodium   |
| Hematocrit   | Potassium  |
| Erythrocyte count (RBC)  | Bicarbonate  |
| Mean cell volume (MCV)   | Chloride   |
| Mean cell hemoglobin concentration (MCHC)                          | Phosphorus   |
| Leukocytes (WBC)   | Total bilirubin  |
| Platelets  | Direct bilirubin   |
| Absolute counts of:   | Alkaline phosphatase   |
| Neutrophils, segmented   | Alanine aminotransferase (ALT/SGPT)                                      |
| Neutrophils, juvenile (bands)                                      | Aspartate aminotransferase (AST/SGOT)                                    |
| Lymphocytes  | Blood urea nitrogen (BUN)  |
| Monocytes  | Uric acid  |
| Eosinophils  | Creatinine   |
| Basophils  | Calcium  |
| Urinalysis (dipstick)a:                          | Glucose  |
| Color  | Albumin  |
| Specific gravity   | Cholesterol (total)  |
| pH   | Total protein  |
| Protein  | Calculated creatinine clearance  |
| Glucose  | Creatine phosphokinase (CPK)   |
| Ketones  | Triglycerides  |
| Bilirubin  | Gamma-glutamyl transferase (GGT)   |
| Urobilinogen   |  |
| Blood  | Lipid Panelc   |
| Nitrite  | Low density lipoprotein (LDL)  |
| Urine creatinine   | High density lipoprotein (HDL)   |
| Leukocyte esterase   | Very low density lipoprotein (VLDL)                                      |
| Other Tests:  |  |
| Human immunodeficiency virus antibody (HIV) f           | Pregnancy test (serum) d                                      |
| Hepatitis B surface antigen (HBsAg) f                   | Follicle-stimulating hormone (FSH) e                          |
| Anti-hepatitis B surface antibody (HBsAb) f             | Thyroid-stimulating hormone (TSH) and free T4                            |
| Anti-hepatitis B core antibody (HBcAb) f                | Ixekizumab serum concentration (pharmacokinetic)                         |
| Anti-hepatitis C antibody f,h                           | Partial thromboplastin time (PTT)  |
| HBV DNA g   | Prothrombin time/international normalized ratio                          |

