### 6.13.4.1. Leukocytes (WBC) and Platelets

Further analyses will be conducted for total leukocytes, neutrophils, platelets, lymphocytes, monocytes, eosinophils, and basophils. Neutrophils will include both segmented neutrophils and absolute neutrophils (derived by adding segmented neutrophils and band neutrophil). The segmented neutrophils and absolute neutrophils will be summarized using the same categories.

Shift table will be produced showing the number and percentage of patients shifting from baseline to a minimum postbaseline result in each relevant category by treatment groups for Periods 2 and Period between Week 0 and Week 16, respectively:

- Scheduled visits, unscheduled visits, and repeat measurements will be included.
- Baseline is defined as the minimum result during the defined baseline period or baseline.
- Use the minimum non-missing postbaseline value within each study period.
- The parameters and categories are:
  - Leukocytes:  $\geq 1 \times \text{LLN}$  (Normal),  $< \text{LLN}$  to  $\geq 3.0 \times 10^9/\text{L}$  (Grade 1),  $< 3.0 \times 10^9/\text{L}$  to  $\geq 2.0 \times 10^9/\text{L}$  (Grade 2),  $< 2.0 \times 10^9/\text{L}$  to  $\geq 1.0 \times 10^9/\text{L}$  (Grade 3), and  $< 1.0 \times 10^9/\text{L}$  (Grade 4).
  - Neutrophils:  $\geq 1 \times \text{LLN}$  (Normal),  $< \text{LLN}$  to  $\geq 1.5 \times 10^9/\text{L}$  (Grade 1),  $< 1.5 \times 10^9/\text{L}$  to  $\geq 1.0 \times 10^9/\text{L}$  (Grade 2),  $< 1.0 \times 10^9/\text{L}$  to  $\geq 0.5 \times 10^9/\text{L}$  (Grade 3), and  $< 0.5 \times 10^9/\text{L}$  (Grade 4)
  - Platelets:  $\geq 1 \times \text{LLN}$  (Normal),  $< \text{LLN}$  to  $\geq 75.0 \times 10^9/\text{L}$  (Grade 1),  $< 75.0 \times 10^9/\text{L}$  to  $\geq 50.0 \times 10^9/\text{L}$  (Grade 2),  $< 50.0 \times 10^9/\text{L}$  to  $\geq 25.0 \times 10^9/\text{L}$  (Grade 3), and  $< 25.0 \times 10^9/\text{L}$  (Grade 4).
  - Lymphocytes:  $\geq 1 \times \text{LLN}$  (Normal),  $< \text{LLN}$  to  $\geq 0.8 \times 10^9/\text{L}$  (Grade 1),  $< 0.8 \times 10^9/\text{L}$  to  $\geq 0.5 \times 10^9/\text{L}$  (Grade 2),  $< 0.5 \times 10^9/\text{L}$  to  $\geq 0.2 \times 10^9/\text{L}$  (Grade 3), and  $< 0.2 \times 10^9/\text{L}$  (Grade 4).
- The above LLNs are defined as:
  - Leukocytes:  $\text{LLN} = 4.0 \times 10^9/\text{L}$
  - Neutrophils:  $\text{LLN} = 2.0 \times 10^9/\text{L}$
  - Platelets:  $\text{LLN} = 150 \times 10^9/\text{L}$

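### Four blood counts are taken out of the treatment-emergent high/low laboratory table, but the analysis that replaces it looks only at low values, so no incidence of counts above the upper limit is produced

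*SAP*

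**What the plan says.** Protocol 9.5.2 states: "Laboratory assessments will be presented as mean changes from baseline and as incidence of treatment-emergent abnormal, high, or low laboratory values". For a high value, which any sample taken after baseline can supply, the definition is: "a change from a value less than or equal to the high limit at all baseline visits to a value greater than the high limit". The protocol names no exceptions, and all four counts are in the haematology panel of Protocol Appendix 3.

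SAP 6.13.4 plans the corresponding table: number and percentage of patients by treatment group, with Fisher's exact test in the Safety Population for Period 2 and for Weeks 0 to 16. Scheduled, unscheduled and repeat samples all count. It then provides that "neutrophils, leukocytes, platelets, and lymphocytes will not be included in the treatment-emergent abnormal, high, or low summary". The hepatic analytes ALT, AST, total bilirubin and ALP are excluded in the same sentence. For the blood counts the reason given is that "a separate analysis addressing leukocytes (white blood cell [WBC]) and platelets is described in Section 6.13.4.1".

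SAP 6.13.4.1 describes a shift table of "patients shifting from baseline to a minimum postbaseline result in each relevant category". Baseline is also the minimum. The categories run from normal, meaning at or above the lower limit of normal (LLN), down to Grade 4. The section's box plot likewise compares minimum with minimum.

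For leukocytes, platelets and the hepatic tests, which it singles out as being of special interest, SAP 6.13.4 also plans a "By-patient listing of abnormal laboratory test results (criteria defined in the shift tables excluding the normal category").

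**The concern.** The reason for taking the four counts out of the high/low table is that another section deals with them. That holds for low values. It does not hold for high values, because nothing in 6.13.4.1 refers to an upper limit. The high half of a protocol commitment is dropped, and the SAP does not say so.

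What is at stake is modest. A regulator or safety reviewer who looks for the proportion of patients per arm with new leukocytosis, neutrophilia, lymphocytosis or thrombocytosis, as defined by laboratory values, will find neither a row nor a test. The incidence table is also the only one of the laboratory summaries showing high values that counts unscheduled and repeat samples. The continuous summaries and general box plots leave those samples out. A count that is high only at an unscheduled visit therefore enters no laboratory summary.

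**Working it through.** The plan gives no figure to reproduce. The check is whether the replacement analysis can register a high value at all.

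**Step 1: the category rules in SAP 6.13.4.1.** Values are ×10⁹/L. Normal means at or above LLN, with no upper bound.

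| Count | LLN | Floors of Grades 1, 2, 3 | Upper limit defined |
|---|---|---|---|
| Leukocytes | 4.0 | 3.0, 2.0, 1.0 | none |
| Neutrophils | 2.0 | 1.5, 1.0, 0.5 | none |
| Platelets | 150 | 75, 50, 25 | none |
| Lymphocytes | 1.1 | 0.8, 0.5, 0.2 | none |

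**Step 2: apply both rules to patients whose counts rise.** The patients are invented. The ULNs are assumptions, since the documents give none: leukocytes 11, neutrophils 7.5, platelets 400, lymphocytes 4. Treatment-emergent high (6.13.4) means maximum baseline ≤ ULN and maximum post-baseline > ULN. The shift (6.13.4.1) is the category of the minimum baseline to the category of the minimum post-baseline.

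| Count | Baseline | Post-baseline | Maximum against ULN | Treatment-emergent high? | Shift on minimum values |
|---|---|---|---|---|---|
| Leukocytes | 6, 7 | 6.5, 18, 9 | 7 ≤ 11, then 18 > 11 | yes | 6 → 6.5: normal to normal |
| Neutrophils | 3.5, 4 | 3.8, 14, 5 | 4 ≤ 7.5, then 14 > 7.5 | yes | 3.5 → 3.8: normal to normal |
| Platelets | 250, 260 | 255, 700, 400 | 260 ≤ 400, then 700 > 400 | yes | 250 → 255: normal to normal |
| Lymphocytes | 1.8, 2 | 1.9, 7, 2.2 | 2 ≤ 4, then 7 > 4 | yes | 1.8 → 1.9: normal to normal |

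All four patients are treatment-emergent high under the definition, and all four are recorded as unchanged in the shift table. A value of 10,000 ×10⁹/L would still be classed as normal. The result does not depend on the assumed ULNs, because the shift table uses no upper limit. Its extra label for an increase does not help either: it compares categories, and none lies above normal.

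**Step 3: look for the high side elsewhere.**

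- The abnormal-results listing takes its criteria from the shift tables without the normal category, so it lists only low values for these counts.
- In Table RHBX.6.8 the cytopenia topic uses leukopenia and thrombocytopenia terms, and the infection listing asks for minimum post-baseline counts.
- The continuous summaries in 6.13.4 (change from baseline to last observation, compared by ANCOVA) and its box plots (quartiles and maximum beneath, reference lines on the observed-value plots) do cover these counts, at scheduled visits.
- The by-patient listing of all laboratory values also covers them.

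None of these counts patients above ULN or compares that count between arms.

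**Step 4: compare with the neighbouring analytes.** The hepatic tests excluded in the same sentence do have a replacement that covers the high side: Table RHBX.6.8 uses the maximum post-baseline value against multiples of ULN. Monocytes, eosinophils and basophils are not excluded, so their high values stay in the table. The bullet just before the exclusion sets the limit rule for that table and singles out the same four counts: sponsor-defined LLN, performing laboratory otherwise. It is odd to set limits in a table for analytes that the next bullet removes from it.

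**The case against.** The strongest reply is that little is lost. A general rise in any of the four counts would show in the ANCOVA of mean change against placebo and in the box plots. Every individual value is listed. Under Protocol 8.4.3 a clinically significant laboratory finding that results in a diagnosis is reported as an adverse event, and SAP 6.13.2 tabulates treatment-emergent events by preferred term with Fisher's exact test, whatever visit they came from. Infections are analysed directly, so a raised leukocyte count adds only an indirect marker. The protocol's stated concern is with low counts: its adverse events of special interest name cytopenias, and its discontinuation criteria and neutrophil monitoring are one-sided. Protocol 9.5 leaves further detail to the SAP, and Protocol 9.2 requires an amendment only when a principal feature changes.

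Most of this stands, and it limits the point. A reader might infer from the exclusion that high counts are never tabulated, or that no comparison with placebo touches them. The documents do not support either reading, for the reasons just given.

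The reply does not supply the missing item. Mean change and box plots do not give the proportion of patients who cross ULN, and they omit unscheduled samples. Adverse event tables capture only findings that led to a diagnosis. A focus on cytopenias explains why 6.13.4.1 was written, but not why the high side was removed. Protocol 9.2 also expects a lesser change in analysis to be described with its justification in the clinical study report. The SAP's revision history mentions only that reference ranges for the white-cell and hepatic parameters were clarified.

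**Conclusion.** The point holds as a limited gap in safety reporting. For leukocytes, neutrophils, lymphocytes and platelets the SAP produces no laboratory-based incidence of treatment-emergent values above ULN. This applies to Period 2, to Weeks 0 to 16 and to the period on ixekizumab rescue. The Fisher comparison planned for the first two is lost with it. That departs from Protocol 9.5.2, and the reason the SAP gives covers only the low side.

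The conclusion rests on the SAP text as written and needs no assumption about how often high counts occur; the documents give no basis for a rate. The contrast with the hepatic analytes and the limit rule in the preceding bullet suggest an oversight rather than a decision, but they do not prove it. Efficacy conclusions, alpha and sample size are unaffected. The change is desirable, not essential.

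**What to change.** In SAP 6.13.4, restrict the exclusion to the low side. Suggested wording: leukocytes, neutrophils, lymphocytes and platelets are excluded from the treatment-emergent low summary (see 6.13.4.1) and retained in the treatment-emergent high summary, using the performing laboratory's ULN. Add values above ULN for these counts to the criteria of the abnormal-results listing. Leave the hepatic exclusions as they are.

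This also removes the conflict with the preceding bullet, whose rule already leaves the upper limit for these counts to the performing laboratory.

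Two alternatives would do: add a maximum-to-maximum shift against ULN in 6.13.4.1, or state the departure from Protocol 9.5.2 and justify it in the clinical study report.

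The cost of the preferred change is four rows in a table that is being programmed anyway, one SAP sentence and one listing criterion. No new data are needed.

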### 6.13.4.1. Leukocytes (WBC) and Platelets

Further analyses will be conducted for total leukocytes, neutrophils, platelets, lymphocytes, monocytes, eosinophils, and basophils. Neutrophils will include both segmented neutrophils and absolute neutrophils (derived by adding segmented neutrophils and band neutrophil). The segmented neutrophils and absolute neutrophils will be summarized using the same categories.

Shift table will be produced showing the number and percentage of patients shifting from baseline to a minimum postbaseline result in each relevant category by treatment groups for Periods 2 and Period between Week 0 and Week 16, respectively:

- Scheduled visits, unscheduled visits, and repeat measurements will be included.
- Baseline is defined as the minimum result during the defined baseline period or baseline.
- Use the minimum non-missing postbaseline value within each study period.
- The parameters and categories are:
  - Leukocytes:  $\geq 1 \times \text{LLN}$  (Normal),  $< \text{LLN}$  to  $\geq 3.0 \times 10^9/\text{L}$  (Grade 1),  $< 3.0 \times 10^9/\text{L}$  to  $\geq 2.0 \times 10^9/\text{L}$  (Grade 2),  $< 2.0 \times 10^9/\text{L}$  to  $\geq 1.0 \times 10^9/\text{L}$  (Grade 3), and  $< 1.0 \times 10^9/\text{L}$  (Grade 4).
  - Neutrophils:  $\geq 1 \times \text{LLN}$  (Normal),  $< \text{LLN}$  to  $\geq 1.5 \times 10^9/\text{L}$  (Grade 1),  $< 1.5 \times 10^9/\text{L}$  to  $\geq 1.0 \times 10^9/\text{L}$  (Grade 2),  $< 1.0 \times 10^9/\text{L}$  to  $\geq 0.5 \times 10^9/\text{L}$  (Grade 3), and  $< 0.5 \times 10^9/\text{L}$  (Grade 4)
  - Platelets:  $\geq 1 \times \text{LLN}$  (Normal),  $< \text{LLN}$  to  $\geq 75.0 \times 10^9/\text{L}$  (Grade 1),  $< 75.0 \times 10^9/\text{L}$  to  $\geq 50.0 \times 10^9/\text{L}$  (Grade 2),  $< 50.0 \times 10^9/\text{L}$  to  $\geq 25.0 \times 10^9/\text{L}$  (Grade 3), and  $< 25.0 \times 10^9/\text{L}$  (Grade 4).
  - Lymphocytes:  $\geq 1 \times \text{LLN}$  (Normal),  $< \text{LLN}$  to  $\geq 0.8 \times 10^9/\text{L}$  (Grade 1),  $< 0.8 \times 10^9/\text{L}$  to  $\geq 0.5 \times 10^9/\text{L}$  (Grade 2),  $< 0.5 \times 10^9/\text{L}$  to  $\geq 0.2 \times 10^9/\text{L}$  (Grade 3), and  $< 0.2 \times 10^9/\text{L}$  (Grade 4).
- The above LLNs are defined as:
  - Leukocytes:  $\text{LLN} = 4.0 \times 10^9/\text{L}$
  - Neutrophils:  $\text{LLN} = 2.0 \times 10^9/\text{L}$
  - Platelets:  $\text{LLN} = 150 \times 10^9/\text{L}$
  - Lymphocytes:  $\text{LLN} = 1.1 \times 10^9/\text{L}$
- With additional categories:
  - Decreased; postbaseline category  $<$  baseline category
  - Increased; postbaseline category  $>$  baseline category
  - Same; postbaseline category = baseline category.

The change from minimum baseline to minimum postbaseline result for each of these leukocytes and platelets will be summarized graphically using a box plot for Periods 2, respectively.

### 6.13.4.2. Neutrophil Follow-Up

Neutrophil counts will be followed throughout the study. Patients will continue in Period 3 until their neutrophil counts have recovered.

The neutrophil follow-up analysis will be conducted on the Neutrophil Follow-Up Population defined as patients who have an absolute neutrophil count  $< 1500$  cells/ $\mu\text{L}$  (SI units:

$<1.5 \times 10^9/L$ ) at the last scheduled visit or ETV prior to entering Period 3 and less than the patient's baseline absolute neutrophil count (that is, prior to first injection at Week 0). These patients are monitored during Period 3 until neutrophil recovery.

Neutrophil clinical recovery is defined as an absolute neutrophil count  $\geq 1500$  cells/ $\mu L$  (SI units:  $\geq 1.5 \times 10^9/L$ ) or greater than or equal to a patient's minimum absolute neutrophil count prior to first study drug injection at Week 0.

If a patient's neutrophil count has not recovered, within 12 weeks after entering the follow-up period (Visit 802), the patient will return for Visit 803 (12 weeks after Visit 802). Additional visits may be required for appropriate patient management depending upon the degree of neutropenia. If at Visit 802, a patient has met the criteria for neutrophil recovery, the patient's participation in the study will be considered complete unless the investigator deems additional follow-up may be necessary.

The number and percentage of patients achieving neutrophil clinical recovery will be presented by treatment groups and week interval for the Neutrophil Follow-Up Population for Period 3. The number and percentage of patients with an absolute neutrophil cell count that is at least 25%, 50%, 75%, or 100% of the patient's baseline absolute neutrophil count (that is, prior to first injection at Week 0), irrespective of absolute neutrophil minimum, will be included in the summary.

